3.5.4 Pharmacokinetic Parameters

The following PK parameters will be determined for the 2 – 17 yrs age groups using a naïve pooled approach on PK Day 1 and Day 2:

 PK analysis of serum iron, corrected serum iron, maltol and maltol glucuronide in the ferric maltol group.

Parameters	Description	Precision
Cmax	Maximum plasma concentration; determined directly from the concentration time profile; if the maximum plasma concentration occurs at more than one time point, C _{max} is defined as the first maximum value	sig/3
T _{max}	Time to C_{max} ; If the maximum value occurs at more than one time point, T_{max} is defined as the first time point with this value.	dec/2
AUClast	Area under the plasma concentration vs time curve (AUC) from predose (time 0) to the last quantifiable plasma concentration (C _{last})	sig/3
AUCinf	AUC from time 0 to infinity; calculated as (AUC _{last} + C _{last} /λz)	sig/3
t _{1/2}	Apparent first-order terminal elimination half-life; calculated as ln(2)/λz	dec/2

Note: "Precision" is defined as the default type (significant figures "sig" or decimal places "dec") and value that will be displayed in outputs unless specifically defined elsewhere.

The Linear-Log Trapezoidal method (equivalent to the Linear Up/Log Down option in WinNonlin) will be used in the computation of all AUC values.

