To assess the impact of a test meal on the PK of ferric maltol, an ANOVA model was performed on the In-transformed PK parameters (C_{max} , AUC_{last} , and AUC_{inf}) of the 2 formulations including terms for sequence (treatment sequence), treatment (formulation/condition), and period as fixed effects, and subjects nested within a sequence as a random effect.

For the capsule formulation, the ratios of C_{max} , AUC_{last} , and AUC_{inf} geometric LS means (90% CI) were 147.27% (130.01, 166.81), 134.25% (121.86, 147.91), and 137.53% (114.45, 165.26), respectively, comparing fasted versus fed conditions. These findings indicate that a food effect was observed for ferric maltol capsule with respect to C_{max} but a definitive food effect was not observed with respect to AUC_{last} and AUC_{inf} .

For the suspension formulation, the ratios of C_{max} , AUC_{last} , and AUC_{inf} geometric LS means (90% CI) were 103.93% (91.75, 117.72), 107.32% (97.41, 118.24), and 96.10% (76.45, 120.79), respectively, comparing fasted versus fed conditions. These findings indicate that the ferric maltol suspension had similar PK when administered in fasted or fed conditions with respect to C_{max} and AUC_{last} .

This Phase 3 open-label, comparative study is in the Paediatric Investigational Plan (PIP), designed to evaluate the safety, efficacy and tolerability of ferric maltol oral suspension compared to ferrous sulfate oral liquid over a 12 weeks treatment period in children and adolescents aged between 2 and 17 years. In order to comply with the iPSP agreed with FDA, children from 1 month to less than 2 years will be included in only the ferric maltol group. Due to the isoform of the glucuronidation enzyme, infants will initially receive only a single dose of ferric maltol. If the data from the single dose in this age group shows evidence of absorption of serum iron and elimination of maltol, subjects will enter a Treatment phase and be assigned to the ferric maltol arm. Subjects will be eligible to enter the treatment phase if the maltol level returns to baseline, or to a low level, confirming there is no accumulation of maltol or maltol glucuronide and there is evidence of iron absorption.

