6 STUDY OBJECTIVES AND ENDPOINTS

6.1 PRIMARY OBJECTIVES:

- To compare the safety and gastrointestinal tolerability of ferric maltol oral suspension and ferrous sulfate oral liquid in children and adolescents aged 2 years to 17 years and assess the safety and tolerability of ferric maltol oral suspension in children 1 month to less than 2 years, in the treatment of iron deficiency anaemia during the 12 weeks treatment period.
- 2. To assess the effect on haemoglobin in children and adolescents aged 1 month to 17 years after twice daily ferric maltol oral suspension administration for 12 weeks

6.2 SECONDARY OBJECTIVES:

- 1. To assess the pharmacokinetics (PK) in children and adolescents aged 2 to 17 years after a single dose of ferric maltol oral suspension on Visit 2 (PK Day 1), and after twice daily administration for at least 6 days, on Visit 3 (PK Day 2), after a single morning dose, through measurement of serum iron, corrected serum iron, transferrin saturation (TSAT) and plasma maltol and maltol glucuronide
- 2. To assess the effect on iron markers in children and adolescents aged 1 month to 17 years after twice daily ferric maltol oral suspension administration for 12 weeks
- 3. To assess the PK, in children aged 1 month to less than 2 years of age after a single dose of ferric maltol oral suspension (Pre-assignment PK visit) and after twice daily administration for at least 6 days, on Visit 3 (PK Day 2), after a single morning dose, through measurement of serum iron, corrected serum iron, transferrin saturation (TSAT) (PK Day 2 only), plasma (PK Day 2 only) and urine concentration of maltol and maltol glucuronide
- 4. To assess the effect, in children aged 1 month to less than 2 years of age after twice daily administration for at least 6 days, on Visit 3 (PK Day 2) after a single morning dose, on serum transferrin, total and unsaturated iron binding capacity (TIBC, UIBC)
- 5. To assess the effect, in children aged 2 to 17 after a single dose of ferric maltol suspension Visit 2 (PK Day 1), and after twice daily administration for at least 6 days, on Visit 3 (PK Day 2) after a single morning dose, on serum transferrin, total and unsaturated iron binding capacity (TIBC, UIBC).
- 6. To compare the palatability from age-appropriate scoring system of ferric maltol oral suspension and ferrous sulfate oral liquid

CONFIDENTIAL Page 40 of 80

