3.4.2 Secondary Endpoints Analysis

The secondary endpoints will be reported for each treatment group using descriptive statistics summarised by mean, median, and range (minimum and maximum), and 95% confidence interval for the mean where applicable, split by age group.

Any measurement obtained after a patient received a blood transfusion, or received an intravenous iron or erythropoiesis stimulating agent (ESA) will be excluded from the analysis.

The secondary endpoints are as follows: PK analysis of Serum Iron, Corrected serum iron, TSAT, Transferrin, TIBC, UIBC, Maltol and Maltol Glucuronide.

Descriptive summary statistics will be summarised for children and adolescents aged 1 month to 17 years in the ferric maltol group for the PK analysis of Serum Iron, Corrected serum iron, TSAT, Transferrin, TIBC, UIBC, Maltol and Maltol Glucuronide.

Changes in iron markers from baseline to Weeks 4 and 12

The secondary analysis of the change from baseline to Weeks 4 and 12 in iron markers (serum iron, serum corrected iron, transferrin, TSAT, TIBC, UIBC and ferritin) will be summarised using descriptive summary statistics. In this analysis, missing Week 12 and Week 4 values will be imputed using a LOCF (last observation carried forward) approach in which the last available post-baseline measurement will be used in the analysis.

Achieving Hb concentration within normal range at Week 12

The number and percentage of subjects achieving normal range, based on the central laboratory's normal reference range, at Week 12 will be summarised by treatment group.

Qualitative assessments from subject questionnaires that allow evaluation of the acceptability, palatability and ease of use

Qualitative assessments from subject questionnaires that evaluate acceptability, palatability and ease of use will be summarised separately for children aged 5 and under and those aged 6 and over.

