0.1 ml/kg ferric maltol under supervision. Three PK Post-dose blood samples will be collected at the following windows 1.0-2.0 hrs, 3.0-4.0 hrs and 10.0-12.0 hrs; postdose urine samples will be taken between 0.5 hr -3 hrs, 3 hrs -6 hrs and 7 hrs -12hrs post dose.

In the event of an administered dose not being consumed or partially consumed by the patient this will be noted as a missed dose and will not be repeated.

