3.5.3 Pharmacokinetic Concentration

The following PK concentrations for the two age groups, 2-17 yrs and 1 m - < 2 yrs, will be determined and the observed values will be summarised by age group, formulation / condition, and by visit/timepoint for PK Population using the following statistics: n (the number of subjects), geometric mean, geometric standard deviation (SD), coefficient of variation (CV), median, minimum and maximum. The observed data will also be listed by age group, formulation / condition group for each individual subject for PK Population.

If the PK data for any age group is too limited and does not support summary statistics, only listings will be provided.

For age group 2-17 yrs, the mean observed plasma concentrations will be plotted on a linear and semi-logarithmic scale against nominal time range, formulation / condition. Geometric mean observed plasma concentrations will also be plotted on a linear scale against nominal time range by formulation/condition.

If the PK data for any age group is too limited and does not support summary statistics (i.e., mean and geomean), only individual concentrations will be plotted.

Individual observed concentrations will be plotted on a linear and semi-logarithmic scale against actual timepoint for each formulation/condition. Due to the sparse collection of data, all individuals within an age group will be plotted on the same plot.

2 - 17 yrs age groups:

 Plasma maltol and maltol glucuronide, serum iron, baseline corrected serum iron, transferrin, transferrin saturation (TSAT), total and unsaturated iron binding capacity (TIBC, UIBC).

1 m - < 2 yrs age groups:

 Serum iron, baseline corrected serum iron, total and unsaturated iron binding capacity (TIBC,UIBC), transferrin, transferrin saturation (TSAT), plasma maltol and maltol glucuronide, urine concentration of maltol and maltol glucuronide.

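### The SAP derives PK parameters only for ages 2–17; for infants it plans concentration summaries alone, short of the protocol's infant PK plan and with no recorded change

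*SAP*

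**What the plan says.** **SAP 3.5.4.** "The following PK parameters will be determined for the 2 – 17 yrs age groups", by a naive pooled approach, on both PK days, for serum iron, corrected serum iron, maltol and maltol glucuronide. Infants are not named.

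**SAP 3.5.3.** Infants are covered for concentrations: "The following PK concentrations for the two age groups, 2-17 yrs and 1 m - < 2 yrs, will be determined". Their list includes serum iron and the iron indices, and "plasma maltol and maltol glucuronide, urine concentration of maltol and maltol glucuronide". There is a fallback: "If the PK data for any age group is too limited and does not support summary statistics, only listings will be provided".

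**SAP 3.4.2.** "Descriptive summary statistics will be summarised for children and adolescents aged 1 month to 17 years in the ferric maltol group".

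**SAP 3.5.1.** For infants on PK Day 2: "Three PK Post-dose blood samples will be collected", in windows of 1–2, 3–4 and 10–12 h, after a pre-dose sample.

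**Protocol 6.2, objective 3.** "To assess the PK, in children aged 1 month to less than 2 years of age", through serum iron, corrected serum iron, TSAT, and maltol and its glucuronide in plasma and urine. The PK endpoint in protocol 6.4 and SAP 2.3.2 covers 1 month to 17 years.

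**Protocol 12.2.2.** For infants it lists urinary amount excreted (Ae) by interval and renal clearance (CLR), at pre-assignment and on PK Day 2.

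**PK sample size.** Protocol 12.1 gives 36 subjects; SAP 2.2.4 gives 24.

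**SAP section 5.** The listed changes concern the analysis populations for Hb and the Week 4 iron markers. PK is not mentioned.

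**The concern.** Infants are the group for which the protocol itself raises a metabolic question. Protocol 5.5 says: "Due to the isoform of the glucuronidation enzyme, infants will initially receive only a single dose of ferric maltol". They are dosed by weight, while older children receive a fixed dose by age band (protocol 5.5.2). Geometric means in three time windows do not give a single exposure figure that can be set against dose or another age group. As written, the study report would contain AUC and Cmax for ages 2–17, who are sampled to 6 h, and none for the group sampled to 12 h. It would also lack the urinary parameters that the protocol promised. Parameters chosen after database lock would be post hoc, although the samples for them were planned from the start.

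**Working it through.** **1. Plan against plan**

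| Item | Protocol | SAP |
|---|---|---|
| Infant PK as objective and endpoint | Yes (6.2, 6.4) | Yes (2.1.2, 2.3.2) |
| Infant concentrations summarised | Yes (12.2.2) | Yes (3.4.2, 3.5.3) |
| Infant Ae, CLR | Listed (12.2.2) | Absent |
| Infant Cmax, Tmax, AUC, half-life | Not listed | Absent (3.5.4 is ages 2–17) |
| PK sample size | 36 = 3 × 12 | 24 = 2 × 12 |
| Change recorded in SAP section 5 | – | No |

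The products reproduce both stated totals. Reading 36 as three age groups including infants is an inference, but it is the only grouping in the protocol that fits.

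**2. Samples per child (protocol 10.8.6)**
- Infants: 1 + 3 = 4 blood samples on one day, up to 12 h.
- Ages 2–17: 1 + 2 = 3 per PK day, up to 6 h; 2 × 3 = 6 over two days.

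Infants have the longest window and the most samples per day, but fewer in total.

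**3. Could an infant AUC be computed?** The documents give no infant half-life or maltol quantification limit, so this rests on assumptions: a one-compartment curve, C(t) ∝ e^(−k·t) − e^(−ka·t), with k = ln 2 / half-life and ka chosen so that Tmax = 1.0 h. Adult values come from protocol 5.4.2 (ST10-01-102): half-life 0.8 h for maltol and 1.1 h for the glucuronide; Cmax 67.3 and 4677 ng/mL.

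Example: glucuronide, k = 0.630, ka = 1.492, samples at mid-window. Concentrations at 0, 1.5, 3.5 and 11 h are 0, 4286.6, 1593.3 and 14.8.
- Linear up: 1.5 × 4286.6 / 2 = 3215
- Log down: (4286.6 − 1593.3) × 2 / ln(4286.6/1593.3) = 5443
- Log down: (1593.3 − 14.8) × 7.5 / ln(1593.3/14.8) = 2532
- Sum = 11,190. The true AUC is (4677/0.3077) × (1/k − 1/ka) ≈ 13,940, so recovery is 80%.
- If the last sample is below quantification (BLQ) and set to missing (SAP 3.5.2): 3215 + 5443 = 8658, or 62%.

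Across the windows:

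| Sample times (h) | Maltol AUC, all samples | Maltol AUC, last BLQ | Glucuronide AUC, all samples | Glucuronide AUC, last BLQ | Observed/true Cmax (maltol; glucuronide) |
|---|---|---|---|---|---|
| 1, 3, 10 | 85% | 67% | 88% | 63% | 100%; 100% |
| 1.5, 3.5, 11 | 78% | 65% | 80% | 62% | 91%; 92% |
| 2, 4, 12 | 66% | 57% | 70% | 56% | 74%; 76% |

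With times uniform within the windows, BID steady state, 10% assay error and 3,000 simulated infants per scenario, median recovery with every sample quantifiable is 77% at half-life 0.8 h, 80% at 1.1 h, 85% at 2 h and 89% at 4 h.

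**4. Is the late sample likely to be quantifiable?** At the adult half-lives the predicted 10–12 h value is a very small share of the peak: 0.106/67.3 = 0.16% down to 0.019/67.3 = 0.03% for maltol, and 27.9/4677 = 0.60% down to 7.9/4677 = 0.17% for the glucuronide. At 4 h the same type of curve at steady state gives about 16–22%. Slow elimination is therefore the case that the schedule captures best.

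**5. Precision with 12 infants.** The 95% CI factor for a geometric mean is exp(2.201 × s/√12), with s = √ln(1 + CV²). For CV 27%, s = 0.265 and the factor is 1.18; for CV 60%, s = 0.555 and it is 1.42.

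**6. CLR.** Renal clearance is Ae over an interval divided by plasma AUC over the same interval. No PK blood is drawn on the pre-assignment day (protocol 10.4), so CLR cannot be derived then. On PK Day 2, AUC0–6 needs interpolation between the 3–4 h and 10–12 h samples.

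**The case against.** Several stronger readings are tempting, and the documents do not support them.

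- *Infants get no exposure measure, or have been dropped from the PK analysis.* SAP 3.5.3 summarises, lists and plots their plasma, serum and urine concentrations, and the PK population in SAP 3.2.4 has no age limit. What is missing is a derived parameter.
- *Each infant has a full dosing-interval profile.* There are three post-dose samples, with nothing between the 3–4 h and 10–12 h windows. In adults, maltol was detectable only up to 4 h (protocol 5.4.2).
- *Blood is drawn from infants in order to compare their exposure with that of older children.* Objective 3 asks for PK through measurement of concentrations; it names neither an AUC nor a comparison.
- *The gap weakens the check on infants before treatment.* That decision uses individual urine results (protocol 9.2), and signs of accumulation suspend recruitment (protocol 7.5). It does not depend on an AUC.

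It is also fair to say that infant AUC would be biased downwards by an amount that depends on half-life, the very quantity in question. Twelve infants is a maximum, and the study may finish without the cohort. The 2–17 values are naive-pooled, one per group, with only sampling Groups 3 and 4 observed beyond 3 h. A comparison between ages is not like for like.

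All of this limits what infant parameters can show. It does not explain why the SAP omits those the protocol lists, or why section 5 is silent.

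**Conclusion.** The point holds as a gap in derived parameters and an unrecorded departure from the protocol. The SAP plans no AUC, Cmax, half-life, Ae or CLR for infants, although the protocol lists the last two and infant PK is a secondary objective. The consequence is for reporting and interpretation, not for the primary endpoints or the infant entry decision.

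Infant AUClast is usable but approximate: about 77–89% of the true value for assumed half-lives of 0.8–4 h, and about 56–67% at the adult half-lives if the last sample is set to missing. With all 12 infants the geometric mean would carry a 95% CI of roughly ×/÷ 1.2 to 1.4 at CV 27–60%; with fewer it would be wider. These figures depend on the assumed curve, which is illustrative and not a fit: its glucuronide AUC of about 13,940 exceeds the reported adult mean of 9651 h*ng/mL at the same Cmax. The textual finding needs none of them.

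**What to change.** 1. Extend SAP 3.5.4 to 1 month to under 2 years on PK Day 2: individual observed Cmax, Tmax and AUClast for plasma maltol, maltol glucuronide, serum iron and baseline-corrected serum iron. Summarise by geometric mean and CV, but arithmetically for corrected iron, which can be zero or negative. Add dose-normalised values. State in advance how few complete profiles would trigger listings only.
2. Restore the protocol's infant Ae, and CLR on PK Day 2 only, or record their removal in SAP section 5. Ae needs urine volumes by interval. Collection details are left to the laboratory manual, so confirm that volumes are recorded.
3. Reconcile 36 with 24, and say whether infants are counted.
4. State the limits: Cmax may be missed because the first post-dose sample is at 1–2 h, and AUClast is approximate. Report how many infants have a quantifiable 10–12 h sample, and show results with and without the others. Label any comparison with the pooled 2–17 values, such as a partial AUC over 0–4 h, as descriptive.

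The cost is SAP wording and one further PK run before database lock. No new samples or visits are needed. The price is a set of infant estimates that must carry these caveats.

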An open-label, Phase I, randomised, 4-way crossover study was completed to evaluate the PK and iron absorption after a single 30 mg dose of ferric maltol administered as a capsule or oral suspension (fasted and fed condition) via primary parameters C_{max} and AUC_{last}.

Both capsule and suspension of ferric maltol in fasted and fed conditions were readily absorbed with mean serum iron concentrations returning to baseline or slightly below at 24 hours.

For the fasted condition, comparing the suspension versus the capsule, the ratios of C_{max} , AUC_{last} , and AUC_{inf} geometric LS means (90% Confidence Interval (CI)) for serum iron findings indicated that, in the fasted condition, ferric maltol capsule and suspension had different PK with respect to C_{max} but a definitive difference in PK was not observed with respect to AUC_{last} and AUC_{inf} .

For the suspension formulation comparing fasted versus fed conditions, the ratios of C_{max} , AUC_{last} , and AUC_{inf} geometric LS means (90% CI) findings indicate that the ferric maltol suspension had similar PK when administered in fasted or fed conditions with respect to C_{max} and AUC_{last} .

For the fed condition, comparing the suspension versus capsule the ratios of C_{max} , AUC_{last} , and AUC_{inf} geometric LS means (90% CI) for serum iron indicate that, in the fed condition, ferric maltol capsule and suspension had similar PK with respect to C_{max} and AUC_{last} and a definitive difference in PK was not observed for AUC_{inf} .

The baseline corrected serum iron and TSAT, were consistent with the primary endpoint findings, although the formulation effect and capsule food effect differences were more marked with baseline corrected serum iron.

It is noted that the overall exposure of maltol and maltol glucuronide are less influenced by physiological iron status compared to the iron PK parameters.

There were no apparent differences between the formulations (suspension versus capsule) in the number of AEs and no study drug-related TEAEs were reported for either formulation.

CONFIDENTIAL Page 27 of 80

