3.1.4 Summary Statistics

Categorical data will generally be summarised with counts and percentages of subjects. The denominator used for the percentage calculation will be clearly defined. Continuous data will

generally be summarised with descriptive statistics including n (number of non-missing values), mean, median, standard deviation, range (minimum and maximum).

For PK parameters, descriptive statistics will also include coefficient of variation (CV %), geometric mean (GM) and GM CV (%).

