3.5 Pharmacokinetic Assessment

3.5.1 Sample Collections for Pharmacokinetic Analysis

PK analysis of serum iron, baseline corrected serum iron, TSAT, transferrin, TIBC, UIBC, maltol and maltol glucuronide in children and adolescents aged 1 month to 17 years in the ferric maltol group.

PK blood sampling in the 2 - 17 yrs age groups:

On PK study Day 1 (Visit 2) and PK study Day 2 (Visit 3) for the first 12 subjects in each age group (2 yrs – 9 yrs, 10 yrs-17 yrs, respectively) who have been randomised to ferric maltol groups have baseline PK blood samples collected immediately prior to ferric maltol dosing (0 hr). Subjects will then have further PK blood samples collected at two (2) additional times between 0.5 hr and 6 hrs after dosing on Visit 2 and 3; the post-dose PK sample time collection windows will be 0.5-1h, 1.0-2.0 hrs, 2.0-3.0 hrs, 3.0-4.0 hrs and 4.0-6.0 hrs. For each individual subject, the post-dose PK blood sampling schedule will be the same on PK Day 1 and PK Day 2. Post-dose blood samples should be collected within the time windows allocated only.

N.B: samples should be taken at least 1.0 hr apart. For each individual subject, the post-dose PK blood sampling schedule will be the same on PK Day 1 and PK Day 2.

PK Sample Schedule	PK Sample Schedule	PK Sample Schedule	PK Sample Schedule	PK Sample Schedule
Scriedule	Group 1	Group 2	Group 3	Group 4
PK Day 1 and PK Day 2	(N=3)	(N=3)	(N=3)	(N=3)
Pre-dose (0h)	X	X	X	X
0.5 – 1 hour	X	X	7	
1 – 2 hours	x		х	
2 – 3 hours		X		X
3 – 4 hours		64	X	
4 – 6 hours				X

Post-dose blood samples should be collected within the time windows allocated only. Samples should be taken at least 1.0 hr apart.

PK blood sampling in the 1 m - < 2 yrs age groups:

Pre-assignment phase: All subjects in 1 m-< 2 yrs age group will enter a 1-day PK assessment day prior to entering the treatment phase. Pre-assignment PK Day, each subject has baseline PK urine samples collected immediately prior to ferric maltol dosing (0 h). Following this, subjects will take a single dose of 0.1 ml/kg ferric maltol under supervision. Three (3) PK urine samples will be taken between 0.5 hr -3 hrs, 3 hrs -6 hrs, and 7 hrs -12 hrs post dose. N.B: samples should be taken at least 1.0 h apart.

PK Day 2 (Visit 3), each subject has baseline PK blood and urine samples collected immediately prior to ferric maltol dosing (0 h). Following this, subjects will take a single dose of

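### SAP 3.5.4 plans AUCinf and terminal half-life for uncorrected serum iron, which settles at a non-zero baseline, from pooled samples ending at 4–6 h

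*SAP*

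**What the plan says.** SAP 3.5.4 derives parameters for the 2–17 year "age groups using a naïve pooled approach on PK Day 1 and Day 2". The list is Cmax, Tmax, AUClast, AUCinf and half-life. It is headed by four analytes: "PK analysis of serum iron, corrected serum iron, maltol and maltol glucuronide in the ferric maltol group". No parameter is reserved for some analytes only. The last two parameters are defined through λz: "AUC from time 0 to infinity; calculated as" AUClast + Clast/λz, and "Apparent first-order terminal elimination half-life; calculated as ln(2)/λz".

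SAP 3.5.1 gives each child a pre-dose sample and post-dose samples "collected at two (2) additional times between 0.5 hr and 6 hrs after dosing on Visit 2 and 3", in four schedule groups of three children per age subgroup.

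The Protocol's account of the adult formulation study (5.4.2, ST10-01-104) reports "mean serum iron concentrations returning to baseline or slightly below at 24 hours".

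SAP 3.1.4 adds a general rule: "For PK parameters, descriptive statistics will also include coefficient of variation", together with the geometric mean and its CV.

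**The concern.** Adding Clast/λz to AUClast assumes that the concentration declines exponentially to zero. Maltol and its glucuronide do that. Uncorrected serum iron declines to the child's own iron level and stays there. The formula then treats endogenous iron as drug still to be eliminated, and the slope behind the half-life is flattened by the same constant.

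A programmer who follows the SAP exactly will produce an AUCinf and a half-life for serum iron that look like properties of the product but move with the baseline iron of whichever children were sampled. The SAP sets no rule for λz (minimum points, fit, maximum extrapolated share) that would cause these values to be withheld. The listings-only fallback in SAP 3.5.3 concerns concentration data that are too limited, which is a different problem.

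A smaller question concerns precision. A naive-pooled analysis gives one value per analyte, group and day, so the CV% and geometric CV of SAP 3.1.4 have nothing to be calculated from.

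**Working it through.** The plan states no figure to reproduce here. The check counts the samples, looks at the limit of the integral, and applies the SAP's formulas to assumed profiles.

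**1. Samples behind λz.** From the schedule table in SAP 3.5.1, at three children per schedule group:

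| Window (h) | Schedule groups | Children per age subgroup | Both subgroups pooled |
|---|---|---|---|
| 0.5–1 | 1, 2 | 6 | 12 |
| 1–2 | 1, 3 | 6 | 12 |
| 2–3 | 2, 4 | 6 | 12 |
| 3–4 | 3 | 3 | 6 |
| 4–6 | 4 | 3 | 6 |

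Protocol 5.4.2 (ST10-01-102) puts the maximal change in adult serum iron at 2 h. The terminal slope therefore rests on about three late windows, filled by partly different children.

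**2. Limit of the integral.** Write C(t) = B + E(t), where B is baseline and E is a rise that decays to zero. Then AUC(0–T) = B·T + a bounded term. With B = 40, the baseline alone adds 40 × 6 = 240 by 6 h and 40 × 24 = 960 by 24 h, and it has no limit. AUCinf of uncorrected iron has no finite value to estimate.

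**3. What the formulas return.** All profile inputs are assumptions; the documents give no paediatric serum iron half-life.
- E(t) = P·[exp(−ke·t) − exp(−ka·t)], scaled so that its peak is P; ke = ln(2)/2 = 0.347 per hour (true half-life 2 h).
- Times are 0 and the window midpoints 0.75, 1.5, 2.5, 3.5 and 5 h.
- AUC is linear-up/log-down, as in SAP 3.5.4. λz is the log-linear slope through the last three points (my choice, since the SAP gives no rule).

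Worked case, B = 40, P = 60, ka = 1.5 per hour:

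| | Uncorrected | Baseline-corrected |
|---|---|---|
| Concentrations | 40, 94.1, 99.3, 88.1, 75.4, 61.4 | 0, 54.1, 59.3, 48.1, 35.4, 21.4 |
| AUClast | 400 | 199 |
| λz (per hour) | 0.144 | 0.326 |
| Clast/λz | 426 | 66 |
| AUCinf | 400 + 426 = 826 | 199 + 66 = 265 |
| Extrapolated share | 426/826 = 52% | 66/265 = 25% |
| Half-life, ln(2)/λz | 4.8 h | 2.1 h |

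The AUCinf ratio is 826/265 = 3.1. Over B 30–60, P 60–150 and ka 1–2 per hour:
- half-life is 2.9–6.4 h uncorrected against 2.0–2.5 h corrected;
- AUCinf is 1.5–5.0 times the corrected value;
- 34–61% of the uncorrected AUCinf is extrapolated.

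**4. Baseline or dose?** At ka = 1.5, with the rise fixed at 60, moving the baseline from 30 to 60 takes uncorrected AUCinf from 657 to 1220. With the baseline fixed at 30, moving the rise from 60 to 150 takes it from 657 to 1004. Both matter.

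**5. Does correction cure it?** In a second assumed set (ka 1.5 per hour), corrected iron gives half-lives of 1.6, 3.2 and 6.7 h for true values of 1.5, 3 and 6 h, so the bias is small. The extrapolated share is still 16%, 40% and 64%. Correction makes AUCinf interpretable, but the 6 h horizon can leave it weak, hence the need for an extrapolation limit.

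**6. CV%.** With one pooled value per analyte, group and day, n = 1. The SD divides by n − 1 = 0, so CV% and geometric CV are undefined.

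**The case against.** The strongest reply is that the interpretable analysis is already planned. SAP 3.5.4 applies every parameter to corrected iron, maltol and maltol glucuronide too, so the defect is two surplus rows for one analyte of four. That is right, and it sets the scope. A reader might infer that AUCinf and half-life are unsound throughout 3.5.4. The documents do not support that: Protocol 5.4.2 gives adult half-lives of 0.8 h for maltol and 1.1 h for its glucuronide, which fit within 6 h of sampling.

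A reader might also infer that uncorrected AUCinf reflects baseline iron and not the dose. Step 4 shows that it reflects both.

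Nor is it settled that only 3 children supply the last window. That is the count per 12-child subgroup. SAP 3.5.3 treats 2–17 years as one PK age group, which gives 6, while the plural in 3.5.4 leaves the pooling unclear.

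The adult study reported AUCinf for serum iron, so there is precedent. The precedent does not supply a finite target. Its intervals (Protocol 5.5) were also wider for AUCinf than for AUClast: 87.36–143.23 against 88.04–106.86 for suspension versus capsule in the fed state, a log-width ratio of 0.494/0.194 = 2.5.

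AUClast of uncorrected iron contains baseline as well: 40 × 5 = 200 of the 400 units in the worked case. This stands. AUClast is at least a finite, observed quantity, but it needs a label saying what it includes.

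On CV%, SAP 3.1.4 is general text, and the CV planned for concentrations in 3.5.3 can be computed. Reading this as an invalid analysis would go too far; analysts would simply leave the cells empty.

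Finally, secondary endpoints are descriptive only (SAP 3.1.5), and no stated decision rule uses these parameters. That limits the consequence but does not make the two rows valid.

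**Conclusion.** The point holds for AUCinf and half-life of uncorrected serum iron in the 2–17 year groups. Following SAP 3.5.4 as written gives an AUCinf with no finite target and a half-life lengthened by endogenous iron. No other section repairs this.

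The direction follows from any stable positive baseline under a decaying rise. The size rests on the assumed profiles: roughly 2.9–6.4 h against 2.0–2.5 h for half-life, and 1.5–5.0 times for AUCinf. These are illustrations, not estimates for this trial.

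The CV% matter is a minor clarification. Neither point reaches beyond the reported PK parameters: the haemoglobin and safety endpoints are untouched.

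**What to change.** In SAP 3.5.4:
- For uncorrected serum iron, report only Cmax, Tmax and AUClast, labelled as including baseline iron.
- Restrict AUCinf and half-life to maltol, maltol glucuronide and, where λz is estimable, baseline-corrected serum iron.
- State the λz rule and a maximum extrapolated fraction above which AUCinf is not reported.
- State whether pooling is by age subgroup or over 2–17 years.

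In SAP 3.1.4, say that CV%, geometric mean and geometric CV do not apply to naive-pooled parameters. If precision is wanted, use a bootstrap over subjects, which works with the planned AUC rule. A Bailer or Nedelman–Jia standard error is an alternative, but it needs AUC to be a fixed-weight sum of time-point means, so the linear-up/log-down rule would have to become linear trapezoidal for that purpose.

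The cost is SAP wording and, if precision is added, a modest amount of programming. No new samples or visits are needed.
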